13.2 CLINICAL LABORATORY MEASUREMENTS

The counts and percentages of the shifts in CTCAE grade from baseline to the worst and last post-baseline grade (not including the 30 post treatment end visit in the evaluation of worst grade at post-baseline) will be presented for each laboratory measure. Descriptive statistics of change and percent change from baseline in laboratory values will be presented by visit. Plots of the shift from baseline to worst post-baseline in selected parameters by treatment arm will be presented. In the case of hemoglobin, a parameter that is hugely affected by transfusions, the percent change over time will be explored in patients who did not have a transfusion in the 90 days prior to informed consent or on study.

Laboratory results (including serum pregnancy) will be provided in a subject list and include at minimum subject id, age, treatment arm, visit, assessment date, laboratory category, laboratory parameter, results and lab units.

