6.5.2 Dosage Management Guidelines for Hematologic Toxicity and Related Complications

Myelosuppression is common in patients with MF and this study allows enrollment of patients with severe cytopenias. Patients with complications of myelosuppression may receive standard supportive care, including transient use of granulocyte-colony stimulating factor for the treatment of febrile neutropenia and red blood cell and platelet transfusion as clinically indicated. Patients receiving pacritinib are not allowed to receive erythropoietin for the treatment of anemia or platelet stimulating factors for the treatment of thrombocytopenia.

Hematology parameters, including CBC, differential, and platelet count will be evaluated at regular intervals during the study. These parameters should be monitored more frequently if clinically required. Patients with a baseline platelet count of $\leq 50,000/\mu$ L must be monitored weekly by central laboratory assessment for the first 8 weeks, then monthly if counts remain $\leq 50,000/\mu$ L. Unscheduled local laboratory test results may be used for assessment and management of patients in real time. Samples collected for local testing must also be submitted to the central laboratory and the results captured in the clinical database.

Table 3 indicates required dose interruptions and modifications for hematologic toxicities and complications such as hemorrhage and febrile neutropenia. Of note, if more than one toxicity is experienced simultaneously, the higher-grade toxicity should determine the dose interruption/modification.

Event	CTCAE Grade	Management/Action
Thrombocytopenia	 ≥ 2 grade decrease in platelets to grade 3 or 4 	 Hold pacritinib for up to 7 days until recovery of platelet count to ≤ grade 2. Restart at the next lower dose level. If at 100 mg QD dose level, discontinue.
	• For patients starting treatment with grade 3 thrombocytopenia who progress to grade 4 thrombocytopenia that lasts at least 14 days or is complicated by hemorrhage or a new platelet transfusion requirement	 Pacritinib may be held for up to 7 days at the treating physician's discretion until recovery of platelets to baseline. Restart either at the same dose or at the next lower dose level.

Table 3	Treatment Toxicit	v and Dosage Mana	agement: Hematologic	Toxicities and Rela	ted Complications
I able J.	Treatment Toxicit	y anu Dusage Mana	igement. mematologic	I UNICILIES ANU INCIA	ieu Complications

Event	CTCAE Grade	Management/Action

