5.2 SAFETY POPULATION

The safety population is defined as all randomized patients who received at least one dose of study treatment.

All safety analyses will be performed using the safety population, and patients in this population will be analyzed according to the treatment actually received. Treatment actually received will be

determined by the treatment initially taken. Safety analyses will provide an indication of potential risk in the exploration to determine the recommended dose of pacritinib for further clinical studies.

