13 SAFETY ANALYSES

Safety analyses include summaries and graphical presentations of treatment emergent adverse events, clinical labs, ECG, vital signs, performance status, and any abnormal findings observed during the performance of physical examinations by treatment received after randomization through the end of assigned study treatment + 30 days.

The primary safety measure for dosage selection is the percentage of patients with CTCAE grade 3/4 cardiac treatment-emergent AEs, CTCAE grade 3/4, hemorrhage treatment-emergent AEs, CTCAE grade ≥ 4 thrombocytopenia toxicity, or CTCAE grade ≥ 4 anemia toxicity. Cardiac and hemorrhage treatment-emergent AEs will be determined using Standardized MedDRA Query (SMQ). See section 9.1 for more details. Thrombocytopenia and anemia will be determined by central laboratory measurement.

All other safety data including TEAEs, death, and clinical laboratory measures will be used as supportive measures for evaluation of pacritinib dose-safety relationship.

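### The one hemoglobin analysis meant to remove transfusion effects selects patients on an on-study transfusion, which a falling hemoglobin causes, so it tends to understate a dose-related fall

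*SAP*

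**What the plan says.** SAP 13.2 describes several laboratory displays.

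- CTCAE grade shifts from baseline to the worst and last post-baseline grade "will be presented for each laboratory measure".
- Change by visit: "Descriptive statistics of change and percent change from baseline in laboratory values will be presented by visit".
- Plots of the shift from baseline to the worst value, for selected parameters.
- One further analysis for hemoglobin, of its percent change across visits. It opens "In the case of hemoglobin, a parameter that is hugely affected by transfusions", and it restricts the patients as follows: "explored in patients who did not have a transfusion in the 90 days prior to informed consent or on study".

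Only the last carries a transfusion restriction. SAP 5.2 states: "All safety analyses will be performed using the safety population". In SAP 13, one of the four parts of the primary safety measure is "CTCAE grade ≥ 4 anemia toxicity", with the source given as follows: "Thrombocytopenia and anemia will be determined by central laboratory measurement". SAP 12.2 2 separately summarises change in transfusion frequency by arm, but only among patients transfused at baseline or on treatment.

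Protocol 6.5.2 lets patients with complications of myelosuppression receive "red blood cell and platelet transfusion as clinically indicated". It sets no hemoglobin threshold, and treatment assignment is open-label (Protocol 5).

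**The concern.** The SAP is right that transfusion distorts measured hemoglobin. Its remedy mixes two conditions of different kinds. No transfusion before consent is a baseline characteristic, and restricting on it leaves the randomised comparison intact. No transfusion on study is an outcome of treatment.

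A patient who enters untransfused, falls on pacritinib and receives blood at Week 20 is removed altogether, including valid Week 4 and Week 12 values. A patient who does not fall is kept. The stronger a dose's effect on hemoglobin, the more of its affected patients leave the display. Because the restriction does not specify red cells, it also removes patients given platelets alone, in a trial that enrols patients with platelet counts of 50,000/µL or less.

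At stake is a supportive view of the dose-safety relationship. The primary measure counts only grade 4 or higher anemia, so smaller dose-related falls show up mainly in supportive displays such as this one.

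**Working it through.** The documents give no expected hemoglobin change, no on-study transfusion rate and no transfusion trigger, so there is no planned figure to reproduce. The size can only be illustrated.

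**Inputs.** From Protocol 1.3.4 (anemia): baseline hemoglobin mean 98.9 g/L, SD 22.0, for 200 mg BID in the earlier phase 3 studies. Assumed: patients enter untransfused at 80 g/L or more; the SD of change is 15 or 10 g/L; transfusion occurs below a trigger T of 80 or 70 g/L. The triggers are modelling devices, not clinical thresholds.

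**Step 1: what the display shows in one arm.** With baseline B and change C ~ Normal(true effect, SD), the retained mean is E[C | B ≥ 80, B + C ≥ T]. Simulation with 2,000,000 draws per setting gives:

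| True mean change (g/L) | Shown, SD 15, T 80 | Deleted | Shown, SD 10, T 70 |
|---|---|---|---|
| 0 | +2.5 | 12% | +0.3 |
| −5 | −1.6 | 17% | −4.4 |
| −10 | −5.6 | 24% | −9.0 |
| −15 | −9.5 | 32% | −13.4 |

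**Step 2: what happens to the contrast between arms.** The trial compares doses, so the within-arm error is not the relevant size: part of it is common to all arms. For one arm at 0 and another at −10:

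- SD 15, T 80: 2.5 − (−5.6) = 8.1 against a true 10, a shrinkage of 19%.
- SD 10, T 70: 0.3 − (−9.0) = 9.3 against a true 10, a shrinkage of 7%.

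A separate run used percent change (the SAP's scale), set the entry floor equal to the trigger, and allowed effects down to −20 g/L. The high-minus-low contrast went from −10.0 to −8.7 points at one end (13%) and from −19.3 to −14.0 at the other (27%). The subset lost 5 to 12% of the lowest-dose arm and 14 to 41% of the highest.

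**Step 3: does the unrestricted summary cure it?** No. In the same percent-scale run, with an assumed lift of 20 g/L after transfusion, the all-patient contrast was −7.7 where the truth was −10.0, and −13.2 where it was −19.3. Both planned hemoglobin-change displays therefore lean the same way, and agreement between them would not be reassuring.

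**Step 4: which replacement works?** Three visits were simulated, with 70% of the variance of change assumed persistent within patient. Transfusion follows any visit below T, so the value at that visit is the last pre-transfusion value. Last-visit means for a true −10 g/L:

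| Method | SD 15, T 80 | SD 10, T 70 |
|---|---|---|
| Never transfused | −5.1 | −8.8 |
| Dropped from visit means after first transfusion | −6.1 | −9.0 |
| Last pre-transfusion value carried forward | −11.6 | −10.5 |

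Dropping patients from later visit means leaves most of the bias, because those means still come from patients not yet transfused. Carrying the last pre-transfusion value forward overstates the fall slightly. For a true 0 it gives −1.1 and about −0.2, so the contrasts are 11.6 − 1.1 = 10.5 and 10.5 − 0.2 = 10.3 against a true 10.

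**The case against.** A reader might infer from the hemoglobin sentence that hemoglobin change is examined only in never-transfused patients, and that the plan as a whole therefore understates dose-related anemia. The documents do not support that. The same SAP section plans change and percent change by visit and grade shifts with no transfusion restriction, and the hemoglobin analysis is described as exploratory. Even if the sentence is read as replacing the general percent-change summary for hemoglobin, the grade shifts and absolute change remain. The primary grade 4 or higher anemia measure, the anemia adverse events by grade and the events leading to dose change (SAP 13 and 13.1) all keep transfused patients. No hypothesis is tested.

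It can also be said that transfusion frequency by arm is already planned. That stands in part. SAP 12.2 2 covers newly transfused patients, but its denominator is patients who were transfused, so it does not give the share of initially untransfused patients in each arm who came to need red cells.

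Finally, the subset is not uniquely misleading, since the unrestricted summary is attenuated at least as much in the illustration. That is correct. It means that falling back on all observed values is no cure; it does not make the subset sound.

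**Conclusion.** The point holds for one exploratory, descriptive display, and it is minor. That display conditions on a post-randomisation event caused by the quantity it measures. If anemia is dose-related, it understates the dose contrast, by about 7 to 19% for a true 10 g/L difference under the assumptions in Step 2, and by up to about 27% on the percent scale with larger assumed effects. The direction follows from the selection rule together with a dose-related fall. The size rests on assumed SDs, assumed triggers and a rule that every patient below the trigger is transfused; only the baseline mean and SD come from the documents. If hemoglobin does not differ by dose, the contrast is not distorted in this model, although each arm would look better than it is.

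It does not follow that dose selection would rest on understated anemia, because the primary safety measure and the adverse-event tables are unaffected.

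**What to change.** Amend SAP 13.2 as follows.

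1. Define the set by pre-treatment status only: no RBC transfusion from 90 days before informed consent to first dose. Naming red cells keeps platelet-only recipients in the set, and running to first dose makes the treatment of screening transfusions explicit.
2. Use each patient's hemoglobin values up to the first on-study RBC transfusion, and carry the last pre-transfusion value forward to later visits. Do not simply drop these patients from later visit means.
3. Beside it, report by arm the number and percentage of this set newly RBC-transfused by Weeks 12 and 24.
4. If the never-transfused display is kept, label it as conditioned on a post-treatment event, show the number excluded per arm, and place it next to the all-patient summary.

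The cost is a few sentences and modest programming. Transfusion data are collected (Protocol Table 1; SAP 10.5), and samples analysed locally at unscheduled visits must also go to the central laboratory (Protocol 9.2), so a value taken shortly before a transfusion should usually be available. No new visits, samples or patients are needed. The downside is that a carried-forward low value can slightly overstate the fall, which a footnote should say.

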13.3 OTHER CLINICAL SAFETY

13.3.1 ELECTROCARDIOGRAM (ECG)

The frequency distribution of abnormal QTcF interval measurements on study (after the first study drug treatment through the last dose of study drug) will also be summarized. That is, the proportion of subjects with the following QTcF intervals will tabulated by timepoint at each visit (including worst and last on treatment values) and treatment arm:

- A measured value > 450 ms
- A measured value > 480 ms
- A measured value > 500 ms
- 0 - <= 10 ms above baseline
- 10 - 20 ms above baseline

- ≥ 20 ms above baseline
- 30 ms above baseline
- > 60 ms above baseline

Plots of the shift in QTcF from baseline to highest on treatment will also be presented for each treatment group.

Finally, a plot of the mean change of the QTcF over time will be presented by treatment arm.

13.3.2 ECHOCARDIOGRAM OR MULTIPLE-GATED ACQUISITION SCAN

Change in the left ventricular ejection fraction (LVEF) assessed on study (after the first study drug treatment through the last dose of study drug) will be summarized. Descriptive statistics of change from baseline in LVEF will be presented by treatment arm at each visit, the last post-baseline assessment, and the worst post-baseline assessment (not including the 30-day post treatment end visit in the evaluation of worst grade at post-baseline). At these visits and by treatment arm, the count and percentage of patients with LVEF values $\leq 50\%$ will also be presented overall and in categories of 50% to 40%, 39% to 20%, and $< 20\%$. Similarly, the count and percentage of patients with decreases in LVEF of $\geq 10\%$ or more will be presented overall and in categories of 10% to 19% and $\geq 20\%$.

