¹ Screening procedures must be completed between Days -35 and -7, before treatment initiation, with the exception of the screening (baseline) MRI or CT scan, which must be parformed between Days -10 and -4								
² Day 1 assessments are required to be performed prior to initiation of study treatment and can be performed up to 24 hours prior to initiation of study treatment. At the baseline visit, all patients will be provided with a prescription (and instructions to fill that prescription) for loperamide (Imodium) or a similarly effective antidiarrheal drug. Patients will be instructed to start taking the prescribed loperamide or other antidiarrheal drug per package and physician instructions as soon as they notice any change in frequency or consistency of bowel movements after starting study treatment.								
³ The study visit at week 4 has a scheduling window of ±3 days; however, all procedures other than MRI or CT should be performed on the same day's visit within ±24 hours. ⁴ The study visits at weeks 12 and 24 have a scheduling window of ±7 days; however, all procedures other than MRI or CT should be performed on the same day's visit within ±24 hours.								

Table 1. PAC203 Study Assessments Calendar²⁰

- ⁵ The End of Treatment visit is scheduled within 7 days after terminating study treatment. A final visit to assess events is scheduled 30 ±3 days after the last dose of study treatment. If treatment ends at a regularly scheduled visit, these procedures may be performed at that time.
- ⁶ Informed consent must be obtained before any study-specific washout. This may require 2 weeks (A 2-week washout will be required for anticoagulation agents, antiplatelet agents (except aspirin doses of ≤ 100 mg/day), strong CYP3A4 inhibitors, strong CYP450 inducers, and QTc prolonging agents) or 28 days if patient was taking any experimental therapies. Patients not requiring washout may sign the Informed Consent Form at any time prior to screening procedures.
- ⁷ Vital signs include blood pressure, pulse, respiratory rate, temperature, and body weight.
- ⁸ Height should be measured only at baseline. Spleen size assessed by physical examination as the distance below the LCM at the midclavicular line.

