- ¹⁷ Baseline symptoms and AEs: Patients will be evaluated from the time of signing the Informed Consent Form through 30 days following last dose of study treatment . Each SAE assessed as related to study treatment or study procedures will be collected through 30 days following last dose of study treatment and will be followed until it is resolved, returns to baseline, stabilizes, or the patient is lost to follow-up, whichever occurs first.
- ¹⁸ Concomitant medications are recorded at the post-24-week follow-up assessments for those patients continuing on pacritinib.
- ¹⁹ Disease directed therapy includes any therapy that is specifically directed at controlling a disease or its symptoms and does not include standard supportive care, i.e. pain medications. Examples include growth factors, cytotoxics, interferons and other targeted agents.
- Study assessments will be performed per schedule until approval of Amendment 6, at which point they cease following the patient's End-of-Treatment, or 30-day post (EOT) visit, as applicable. All patients will require End of treatment visit, however, patients who continue to receive pacritinib under expanded access will not require a 30 Day Post EOT visit.
- ²¹ Following approval of Amendment 6, patients who continue to receive pacritinib under expanded access will not require a 30 Day Post EOT visit.

Special Cases: Modifications to Study Assessments Calendar

All patients should complete all visit procedures through Week 24, including patients who stop pacritinib treatment or have protocoldefined progressive disease prior to week 24, unless patient:

- withdraws consent
- dies
- undergoes splenic irradiation, splenectomy, or initiates any non-protocol-directed anti-myelofibrosis treatment

*Patients who continue on pacritinib after Week 24 will receive efficacy and safety assessment every 3 months up to 2.5 years (with the exception of MRI/CT spleen assessment, which will only be followed up to 2 years and TSS assessment, which will only be followed up to 48 weeks). Study assessments will be performed per schedule until approval of Amendment 6, at which point they cease following the patient's End-of-Treatment, or 30-day post (EOT) visit, as applicable.

Patients who discontinue pacritinib treatment prior to Week 24 must complete the *End of Treatment* visit within 7 days of stopping the drug and *30 Day Post End of Treatment* visit within 30 days of *End of Treatment* visit.

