Patients who discontinue pacritinib treatment prior to Week 24, with or without disease progression, will continue to follow this Study Assessments Calendar through Week 24.

Patients who undergo splenic irradiation, splenectomy, or who initiate any non-protocol-directed anti-myelofibrosis treatment at any time must complete the *End of Treatment* visit within 7 days of stopping the drug and *30 Day Post End of Treatment* visit within 30 days of *End of Treatment* visit, but will not complete any additional visits.

If an arm is closed, patients randomized to that arm will end pacritinib treatment and complete the *End of Treatment* visit within 7 days of stopping the drug and *30 Day Post End of Treatment* visit within 30 days of *End of Treatment* visit.

Unscheduled visits should include physical examination, laboratory tests, and radiographic evaluations as clinically indicated in the judgement of the investigator and these results must be entered into the EDC.

Additional visits may be required for patients with baseline platelet count $\leq 50,000/\mu$ L as well as patients who have pacritinib dose modifications due to hematologic, cardiac, diarrhea, or other non-hematologic toxicities in addition to those specified in Section 6.5. Samples drawn for clinical laboratory assessments at unscheduled visits should be submitted to the central laboratory for analysis in addition to any local analysis that may be performed for the purpose of patient management. See Section 6.5 for details.

Abbreviations

Abbreviation	Full Term
AE	adverse event
ALT	alanine aminotransferase (syn: see SGPT)
ASCT	allogeneic stem cell transplantation
AST	aspartate aminotransferase (syn: see SGOT)
AUC	area under the curve
AUC _{inf}	area under the curve to infinite time
AUC _{0-t}	area of the curve up to the last measurable concentration
BAT	best available therapy
BID	twice per day
BUN	blood urea nitrogen
CBC	complete blood count
C _{max}	maximum concentration observed
C _{min}	minimum concentration observed
CRF(s)	case report form(s)
СТ	computed tomography
CTCAE	Common Terminology Criteria for Adverse Events
CYP450	cytochrome P450
DIPSS	Dynamic International Prognostic Scoring System
ECG	electrocardiogram
ECOG	Eastern Cooperative Oncology Group
eCRF	electronic case report form
EDC	electronic data capture
EPs	erythroid progenitors
ET	essential thrombocythemia
FAS	Full Analysis Set
FDA	Food and Drug Administration
FLT3	fms-like receptor tyrosine kinase 3

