7.1.1.1 Spleen Volume

MRI is the preferred modality; CT scan will be used for patients who cannot undergo MRI, or for whom MRI is not available. Imaging should be performed without contrast agent. For each patient, the same imaging modality should be used throughout the study.

Spleen volume will be measured by MRI (preferred) or CT at screening and at the end of weeks 12 and 24 visits. Spleen volume will also be measured at the end of treatment if this does not occur at the end of

Week 24. For patients who continue on pacritinib past Week 24, spleen volume will be assessed by MRI or CT every 3 months up to 2 years. Patients who discontinue treatment (except withdraw of consent or death) will be required to complete the end of treatment visit within 7 days of stopping treatment. Unscheduled imaging studies may be performed at physician discretion if he/she considers disease-related symptoms to be worsening. All images generated as part of unscheduled evaluations must be submitted by the investigator for central review. An independent radiologist, blinded to all patient and site identifiers and treatment assignments, will measure spleen volume. While images generated as part of unscheduled visits may be read locally if treatment discontinuation is being considered, only the scheduled centrally read images will be used for the efficacy analysis.

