Excluded TSS evaluation of treatment effects (GEE analysis) and the dose response using the moving average.	The primary aim of this study is to establish the optimal dose with no plan for a formal statistical hypothesis testing. GEE analysis is not considered integral to evaluate the study efficacy objectives
Excluded '30 day Post-EOT' visit from the evaluation of 'worst' value at post-baseline	Safety measures are focused on assessments performed while on study treatment or within 30 days after treatment ended.
Exclusion of the Interim Analysis	The implementation of the BPP futility rule in PAC203, based on spleen volume reduction (SVR), was flawed as assumptions for SVR were based on response rates observed in the completed Phase 3 studies. This misrepresents the population under study in PAC203. For instance, some patients in the PERSIST-2 population had prior JAK inhibitor exposure, however all patients enrolled in the PAC203 study must have prior JAK inhibitor exposure.

	Following mid-year 2018 meetings with the FDA and EMA, and in consultation with the IDMC, the interim efficacy analysis based on a BPP futility rule of SVR was removed so that the study objective of identifying an optimal dose is informed by efficacy, safety, pharmacokinetic and pharmacodynamic data from a fully enrolled study.
Expanded the analysis windows of the SPV, TSS and PGIC	To minimize missing data while keeping clinical relevance.
Expanded the windows of the labs and vital signs information	A modification to the 'EOT' and '30 day-post EOT' analysis windows was made to align the safety assessments with the visit schedule as specified in the protocol calendar of assessments.
Added ECG categories and plots	Following the E14 clinical evaluation of QT/QTc interval prolongation and proarrhythmic safety guidelines
Added information to the prior and concomitant medication definitions section	Added the definitions for prior and concomitant medications and specified reports by myelofibrosis indication
Added ECOG definition and reports	Added information on the EGOC scale and the definition for each category. In addition added the summary reports.
Added PGIC and spleen variables definitions	These efficacy variables were not defined previously in the document however analyses of this information was specified in the protocol.
Subgroups of Efficacy	Clarification of clinically meaningful groups

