11.2.5 CARDIAC EJECTION FRACTION ASSESSMENT

All patients will have ejection fraction (echocardiogram or MUGA scan) at screening, the end of Week 4, the end of Week 12, the end of Week 24 or the end of treatment visit, and every 6 months while in the follow-up period, and 30 days after the last dose of study treatment.

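### SAP 13.3.2 contradicts itself on the LVEF period: it stops at the last dose, yet excludes the 30-day visit from the worst value only, so End of Treatment tests may drop out

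*SAP*

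**What the plan says.** - **SAP 13.3.2** summarises LVEF change "assessed on study (after the first study drug treatment through the last dose of study drug". The summaries are by arm at each visit, at the last post-baseline assessment and at the worst post-baseline assessment, with counts by LVEF category at the same points. A parenthesis attached to *worst* adds: "not including the 30-day post treatment end visit in the evaluation of worst grade at post-baseline".
- **The SAP modification table** gives the reason for that exclusion: "Safety measures are focused on assessments performed while on study treatment or within 30 days after treatment ended".
- **SAP 11.2.5** lists these ejection fraction times: "the end of Week 4, the end of Week 12, the end of Week 24 or the end of treatment visit". Besides these it has a screening test, a half-yearly test in follow-up, and one 30 days after the last dose.
- **Protocol Table 1, footnote 5:** "The End of Treatment visit is scheduled within 7 days after terminating study treatment". The procedures may be done at a scheduled visit if treatment ends there. Protocol 7.1.1.1 says that patients who discontinue, other than by death or withdrawal of consent, "will be required to complete the end of treatment visit within 7 days of stopping treatment".
- **Protocol, Special Cases after Table 1:** patients who stop before Week 24 "will continue to follow this Study Assessments Calendar through Week 24".
- **Protocol Table 1, footnote 20:** "patients who continue to receive pacritinib under expanded access will not require a 30 Day Post EOT visit".
- **Analysis windows:** SAP Tables 5 and 6 give laboratory data and vital signs an EOT window from the last dose to 15 days later. The SAP's closing table of analysis windows covers spleen volume, TSS and the global impression. LVEF has no window.

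**The concern.** The two instructions in 13.3.2 cannot both be doing work. If the period ends at the last dose, the 30-day visit is already gone from every row and need not be removed from *worst*. If it has to be removed from *worst* only, then data after the last dose must be in the other rows. Two programmers could build different tables from the same paragraph.

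The practical exposure is the EOT test. Scheduled LVEF tests are sparse, so for a patient who stops between visits EOT is the scheduled measurement that covers the final stretch on drug. Section 13.3.2 is the SAP's only by-arm summary of LVEF, in a dose-selection study whose data monitoring committee is told to focus on cardiac events among others.

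**Working it through.** The plan states no figure to reproduce. The check asks which permitted visit days survive each possible cut-off. Let *d* be days after the last dose.

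**Inputs**
- Literal cut in SAP 13.3.2: keep *d* ≤ 0.
- EOT visit, Protocol Table 1 footnote 5: *d* = 0 to 7 (8 days), taking treatment as terminated on the last-dose day. If a 7-day hold (Protocol 6.5.1) comes first, the latest day is 7 + 7 = 14.
- 30-day visit, footnote 5: 30 ± 3 days after the last dose, so *d* = 27 to 33 (7 days).
- 30-day visit, Protocol 7.1.9: 30 ± 3 days after EOT, so *d* = 0 + 27 to 7 + 33 = 27 to 40 (14 days).
- The Special Cases text puts this visit within 30 days of the EOT visit, with no lower limit.

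**Step 1: days kept under each cut-off**

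| Cut-off | EOT (0–7) | 30-day, from last dose (27–33) | 30-day, from EOT (27–40) |
|---|---|---|---|
| Last dose (*d* ≤ 0) | 1 of 8 | 0 of 7 | 0 of 14 |
| Last dose + 15 | 8 of 8 | 0 of 7 | 0 of 14 |
| Last dose + 30 | 8 of 8 | 4 of 7 | 4 of 14 |

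Under the literal cut no 30-day visit survives, so excluding it from *worst* changes nothing. Only a same-day EOT test survives; days 1 to 7 are lost. The last row also shows that a limit of last dose + 30 days would cut off some 30-day visits, so the period should end at the visit, not at a day count.

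**Step 2: a patient who stops early.** Take a last dose on Day 20. EOT is due on Days 20 to 27 (*d* = 0 to 7). The continuing calendar visits on nominal Days 28, 84 and 168 fall at *d* = 8, 64 and 148. Under the literal cut none of these counts, and the patient has no scheduled post-baseline LVEF in the table unless EOT was done on Day 20 itself.

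**Step 3: stretch of exposure left uncovered.** With tests on nominal Days 28, 84 and 168, the most final exposure that can go without a scheduled LVEF in the table is 28 − 1 = 27 days (stop before Week 4), 84 − 28 = 56 days (Weeks 4 to 12) or 168 − 84 = 84 days (Weeks 12 to 24). These are maxima on nominal days. They come from the visit schedule once EOT is removed and ignore the visit windows.

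**Step 4: would the laboratory window alone settle it?** No. In Step 2 the Week 4 test at *d* = 8 lies inside last dose to + 15, possibly beside the true EOT test. A window by itself does not say which one is EOT.

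**The case against.** The strongest reply is that the loss depends on one reading. If the parenthesis on *worst* shows that data after the last dose were meant to be included, EOT is already in. If the cut is deliberate, this is an on-treatment analysis with a redundant parenthesis, perhaps carried over from SAP 13.2, where laboratory data have the same exclusion without the last-dose cut. This stands in part: the documents show a contradiction to reconcile, not that data will be lost. It does not remove the contradiction.

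Some supporting text is also weak. The modification table explains a change and is not an analysis rule; SAP 11.2.5 is a collection schedule; and the introduction to SAP 13, which runs to the end of treatment + 30 days, does not name LVEF. All of that is correct. The point rests on 13.3.2 alone, and the other passages only suggest intent.

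A reader might infer three stronger things that the documents do not support.
- **That cardiac harm would be hidden.** Cardiac TEAEs are collected to 30 days after the last dose and summarised by arm (SAP 11.1 and 13.1). Clinically significant changes on cardiac monitoring are AEs (Protocol 9.1.1). Study data are listed by subject (SAP 6.1). The primary safety measure does not use LVEF values.
- **That a known share of patients is affected.** The drop-out allowance in SAP 16 is not a rate of stopping between visits with a later EOT test, and deaths and consent withdrawals are exempt from EOT under Protocol 7.1.1.1.
- **That QTcF has the same fault.** SAP 13.3.1 uses the same cut, and the SAP 13 introduction does name ECG. But 13.3.1 labels its worst and last values as on treatment, so the cut is consistent there and may be deliberate.

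**Conclusion.** The point holds as an internal contradiction in SAP 13.3.2 with a definite consequence on the literal reading: of the eight permitted EOT days only the last-dose day is kept, and the visit, *last* and *worst* rows all lose the rest. A patient who stops before Week 4 may then have no scheduled post-baseline LVEF in the table.

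The number of patients affected and the direction of any bias cannot be derived from the documents. For scale only, one patient moves a category by 1/50 = 2 percentage points if an arm has 50 patients with a value. The tables are descriptive and no hypothesis is tested. This should be corrected before the tables are programmed, but it does not threaten the study's main safety comparison. The conclusion assumes that EOT takes place on the days the protocol allows and that the SAP's stated period is applied as written.

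**What to change.** Change SAP 13.3.2 only:

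1. Replace the end of the period (the last dose) with the 30-day post-treatment visit.
2. Identify the EOT and 30-day tests by the recorded visit name. This also avoids depending on the protocol's differing anchors for the 30-day visit. Only when no EOT visit is recorded, use the SAP's existing window of last dose to + 15 days and take the test closest to the last dose.
3. Show EOT and the 30-day visit as visit rows. Count EOT toward *worst* and *last*. Keep the 30-day visit out of *worst* only, as the paragraph already says.
4. Show calendar visits attended after stopping treatment, other than EOT, in a separate off-treatment row outside *worst* and *last*. Some of these fall after the 30-day visit, so state that this row is additional to the period in item 1.

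No change is required to 13.3.1.

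The cost is a few sentences and table rows, with no new data. The downside is that some EOT values will have been taken up to a week after the last dose, or later if a hold came first. *Last* will also mix EOT and 30-day values, because patients who move to expanded access have no 30-day visit; the separate EOT row lets the reader see them apart.
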